### 7.1.2 Assessments During Treatment

Subjects have scheduled study visits on Days 1, 2, 8, 15, and 22 of Cycle 1. Thereafter, study visits will occur once per cycle on Day 1 ( $\pm$ 2 days) of each cycle, continuing through Cycle 12 unless otherwise indicated. After Cycle 12, study visits will occur once every 2 cycles (ie, Cycle 12, 14, 16, etc). Refer to the Schedule of Assessments ([Appendix 4](#)) for a complete list of procedures performed at each of the scheduled study visits.

**Concomitant Medications and Therapy:** Concomitant medications and therapy will be recorded at each visit; refer to [Section 6.7](#).

**Adverse Events:** The definition for an AE is provided in [Section 9.2.1](#). All medical occurrences from the time of the first administration of study drug that meet this definition must be recorded. Important additional requirements for reporting SAEs are included in [Section 9.3.3](#). Adverse events will be recorded at each visit, or as they occur during the treatment period.

**Physical Examination, Vital Signs, and Weight:** Symptom-directed PEs will be performed during the treatment period. Vital signs and weight (refer to [Section 7.1.1](#)) will be measured and recorded at each study visit unless otherwise indicated.

**ECOG Performance Status:** The ECOG will be measured and recorded at each study visit unless otherwise indicated. The ECOG index is provided in [Appendix 1](#).

**Neuropathy and Bone Pain Assessments:** Subjects will complete questionnaires for neuropathy and bone pain on Day 1 of Cycles 2, 4, 6, 8, 10, and 12. Neuropathy and bone pain assessments are not required after Cycle 12.

**Bone Marrow Aspirate and Biopsy:** A unilateral bone marrow aspirate and biopsy documenting percent marrow involvement will be repeated as necessary to document response status as clinically indicated. Analysis of bone marrow for confirmation of CR should include staining for CD138 and  $\kappa/\lambda$  mono-clonality by immunohistochemistry or immunofluorescence.

A unilateral bone marrow aspirate sample will also be collected following confirmed disease progression and can be performed any time prior to the start of a new antineoplastic treatment. Refer to [Section 4.3](#) for description of testing.

**Hematology:** Hematology parameters will be measured on Days 1, 2, 8 and 15 of Cycle 1. Thereafter, blood samples for these tests will be collected at each study visit unless otherwise indicated. Hematology parameters must include complete blood count (CBC) with differential and platelet counts. Testing will be performed at the study center's local laboratory or other clinical laboratory listed on the investigator's Form FDA 1572.

**Serum Chemistry:** Serum chemistry parameters will be measured on Days 1, 2, 8, and 15 of Cycle 1. Thereafter, blood samples for these tests will be collected at each study visit unless otherwise indicated. Chemistry parameters must include albumin, alkaline phosphatase, ALT, AST, bicarbonate, blood urea nitrogen, calcium, chloride, creatinine, glucose, lactate dehydrogenase, magnesium, phosphate, potassium, sodium, total bilirubin, total protein, and uric acid. Testing will be performed at the study center's local laboratory or other clinical laboratory listed on the investigator's Form FDA 1572.

**Pharmacokinetics:** Refer to the laboratory binder for instructions on collecting and processing these samples. All subjects regardless of cohort will have PK samples collected and processed as described in the tables below. Additional PK samples will be collected for subjects in Cohort 1 and Cohort 3 who have started dexamethasone. The actual time (versus requested time) at which each sample is drawn must be recorded using a 24-hour format. The same clock should be used for recording the time of dosing. Refer to the laboratory manual for instructions on collecting and processing these samples.

**Table 4: PK Sample Schedule for All Subjects - Cycle 1**

Cycle	Day	Predose	Postdose a				
			1 h ± 15 min	2 h ± 15 min	4 h ± 30 min	7 h (± 1 h)	24 h (± 4 h)
1	1	X	X	X	X	X	X
	8	X	X	X	X	X	
	15	X		X			
	22	X		X			

a. Record actual time of sample collection.

**Table 5: PK Sample Schedule for Cohorts 1 and 3 Subjects Starting Dexamethasone after PD**

Cycle	Day	Predose	Postdose a				
			1 h ± 15 min	2 h ± 15 min	4 h ± 30 min	7 h (± 1 h)	24 h (± 4 h)
X	3 or 4	X	X	X	X	X	X
	11 or 12	X	X	X	X	X	X

a. Record actual time of sample collection.

**Table 6: PK Sample Schedule for Cohorts 4 Expansion**

Cycle	Day	Predose	Postdose a				
			1 h ± 15 min	2 h ± 15 min	4 h ± 30 min	7 h (± 1 h)	24 h (± 4 h)
1	1	X b	X	X	X	X	X
	8 c	X b	X	X	X	X c	X
2	1 d	X b	X	X	X	X b	X

a. Record actual time of sample collection.

b. Additional samples will be collected at screening and following time-points described in the table for the analysis of 4-β-hydroxycholesterol (CYP3A induction maker)

c. On C1D8 Dexamethasone will be administered after the 7 hr postdose PK draw

d. On C2D1 Dexamethasone may be given concomitantly with PCI-32765

The actual time (versus requested time) at which each PK sample is drawn must be recorded using a 24-hour format. The same clock should be used for recording the time of dosing.

**Bone Radiological Assessment:** Repeated bone radiological assessments on study are not mandated by the protocol, but should follow institutional guidelines. Bone radiological assessment includes a lateral radiograph of the skull, antero-posterior and lateral views of the spine, and antero-posterior views of the pelvis, ribs, femora, and humeri.

**Myeloma-Specific Tests:** Myeloma-specific tests include M-protein quantification by SPEP and UPEP, as well as quantitative immunoglobulins, Serum Free Light Chain (Freelite®), and β2-microglobulin. UPEP is performed on a timed urine collection and should be recorded normalized to 24 hours. Urine creatinine determinations should be performed as well as UPEP on all urines collected for M-protein quantification.

Myeloma-specific protein tests will be obtained at the beginning of each cycle. These will include SPEP, UPEP, or SFLC (if measurable disease is present at baseline by these methods), quantitative immunoglobulins and β2-microglobulin. If the M-protein is not measurable by either SPEP or UPEP that test may be omitted at subsequent visits. If the M-protein is or becomes immeasurable by both methods, Serum Free Light Chain (Freelite®) determinations will additionally be performed at all visits thereafter. Testing will be performed at the study center's local laboratory or other clinical laboratory listed on the investigator's Form FDA 1572.

Measurable disease parameters (by serum and urine) must be repeated on Cycle 1 Day 1 prior to study drug administration unless performed within 5 days prior to the start of treatment. After Cycle 1, myeloma specific protein tests may be performed within  $\pm 2$  days of Day 1 of subsequent cycles.

**Cytokines and Chemokines:** Blood samples for serum cytokine and chemokine measurement will be collected on Days 1, 2, 8, and 15 of Cycle 1 and Day 1 of Cycles 2, 3, 4, 6 and 10. Testing will include IL-6, SDF-1, RANKL and MIP-1 $\alpha$ . Centralized testing will be performed at Pharmacyclics LLC using overnight shipped samples.

**Peripheral Blood Immunophenotyping by Flow Cytometry:** Blood samples for immunophenotyping of peripheral blood mononuclear cells will be collected on Days 1, 2, 8, and 15 of Cycle 1 and on Day 1 of Cycles 2, 3, 4, 6 and 10. Markers may include, but are not limited to, CD138, CD19, CD3, CD45, and CD38. Centralized testing will be performed at Pharmacyclics LLC using overnight shipped samples. Refer to the laboratory manual for instructions on collecting and processing these samples.

**Tests of Bone Turnover:** Bone turnover measurements will occur on Cycle 1 Days 1 and 15, Cycles 2, 3, and 4 Day 1; thereafter, they will be performed on Day 1 of the even numbered cycles. Testing will include serum C-terminal cross-linking protein of type-1 collagen (serum CTX, CPT Code: 82523) and urinary N-terminal cross-linking peptide of type-1 collagen (urinary NTX, CPT Code: 82523; 82570). Testing will be performed at a central laboratory. Refer to the laboratory manual for instructions on collecting and processing these samples.

**Confirmation of Responses:** Starting with Cycle 2, subjects will be evaluated for disease response criteria as detailed in [Appendix 5](#). Some or all of the following assessments may be required to confirm the response categories MR, PR, VGPR, CR, and sCR:

- M-protein evaluations:
  - UPEP and SPEP
  - Serum IFE
  - Serum FLC
- Plasmacytoma evaluation
- Bone radiological assessment
- Bone marrow aspiration and biopsy
- Serum chemistries including calcium and albumin

**Plasmacytoma Evaluation:** Subjects with an extra-medullary plasmacytoma that is known or detected at baseline should be monitored throughout the study using the same technique used to evaluate at screening or baseline. Therefore, a subcutaneous plasmacytoma that is readily measurable on physical examination should be followed by repeated physical examination,

with a CT or other clinically appropriate imaging study required only as needed to document CR. Follow-up of a deeply situated extra-medullary plasmacytoma should be in accordance with institutional guidelines, an appropriate imaging study is required to document a clinical response of PR or better.

### 7.1.3 Safety Follow-up Visit

Each subject should be followed for 30 ( $\pm$ 7) days after the last dose of PCI-32765 or prior to the start of a new antineoplastic treatment to monitor for resolution or progression of AEs and to document the occurrence of any new AEs. The procedures required at the Safety Follow-up visit are presented in the Schedule of Assessments ([Appendix 4](#)).

A bone marrow aspirate sample at the time of confirmed progression may be collected during the Safety Follow-up visit or at any time prior to the start of a new antineoplastic treatment. Refer to [Section 4.3](#) for description of testing.

### 7.1.4 Follow-up for Progression and Survival

Subjects who discontinue from the study treatment for reasons other than PD will be followed for Response Follow-up (RFU) approximately every 2 months until PD or start use of alternative antineoplastic therapy. During this period, the following tests may be performed at the investigator's discretion as standard of care:

- M-protein evaluations:
  - UPEP and SPEP
  - Serum IFE
  - Serum FLC
  - quantitative immunoglobulins
- Plasmacytoma evaluation
- Bone radiological assessment
- Serum chemistries including calcium and albumin

A bone marrow aspirate sample at the time of confirmed progression will be collected during this period prior to the start of a new antineoplastic treatment. Refer to [Section 4.3](#) for description of testing.

A minimum of one Long Term Follow Up visit will be performed. Further Long-term Follow-up assessments will no longer be collected.

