**Stage 2:**

- If  $\geq 3$  CBRs are observed within Cohorts 2, 3, or 4 in Stage 1, the Cohort(s) may be selected for expansion for up to a total of enrollment of 43 subjects or until observing  $\geq 8$  CBRs, whichever occurs earlier.
- If there is concurrent Stage 2 enrollment to more than 1 Cohort at any given time, Sponsor will implement centralized assignments into cohorts.

Sponsor maintains the prerogative to select regimen which gives optimal efficacy and safety results at interim analysis for further development while suspend other cohorts at any time.

The expected total enrollment including Cohort 1 is between 67 (minimal) and 164 subjects.

The dose cohorts are summarized in the table below.

Cohort	PCI-32765 (mg/day)	Dexamethasone	Planned First Stage Enrollment	CBR Criteria for First Stage	Total Enrollment (First and Second Stages)
1	420	Upon PD, 40 mg once weekly is allowed†	11*	$\geq 2$	35
2	560	40 mg once weekly	18	$\geq 3$	43
3	840	Upon PD, 40 mg once weekly is allowed†	18	$\geq 3$	43
4	840	40 mg once weekly	18**	$\geq 3$	43

\* n=11 planned for Cohort 1 First Stage, n=13 were enrolled. The decision for second stage expansion will be based on the number of CBR in the first 11 subjects.

\*\* n=18 planned for Cohort 4 First Stage, n=20 were enrolled. The decision for second stage expansion will be based on the number of CBR in the first 18 subjects

† For Cohorts 1 and 3 subjects who have confirmed PD, and who are clinically stable, without significant worsening of symptoms or hematologic status (ie, meet all entry criteria for the study in regard to symptoms and hematology), will be eligible to receive dexamethasone 40 mg orally once per week in addition to continued treatment with PCI-32765, at the discretion of the investigator.

Disease progression (PD) and response assessment will be performed by the investigators using the modified IMWG response criteria ([Appendix 5](#)).

Subjects will otherwise continue on study drug until PD, withdrawal of consent, or until discontinuation of study drug due to an adverse event (AE). Continued treatment with study drug will be allowed for as long as a subject receives benefit.

	
Subjects who discontinue study drug without PD will be followed for response until PD or start use of alternative antineoplastic therapy. Subjects who discontinue treatment due to PD will be followed for survival.

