Serum Free Light Chain (Freelite ® )	X	X					Repeat every cycle if M protein initially or becomes not measurable by protein electrophoresis														X	X	
M-Protein (SPEP or UPEP) f	X	X					X	X	X	X	X	X	X	X	X	X	X	X	X				
Cytokines/Chemokines g		X	X	X	X		X	X	X		X					X				X			
Peripheral Blood Cellular Immunophenotyping h		X	X	X	X		X	X	X		X					X				X			
Bone Turnover Tests (serum CTX and urine NTX)		X			X		X	X	X		X		X			X				X			
Confirmation of Response u							X	X	X	X	X	X	X	X	X	X				X			
Plasmacytoma Evaluations	X	As clinically indicated v																					
Long-term Follow-up Status																					X		

Abbreviations: aPTT = activated partial thromboplastin time; CR = complete response; CT = computed tomography, CTX = C-terminal cross-linking protein of type-1 collagen; ECG = electrocardiogram; FLC = free light chain; IFE = immunofixation; Ig = immunoglobulin; INR = international normalized ratio; ECOG = Eastern Cooperative Oncology Group; LTFU = long-term follow-up; MM = multiple myeloma; MR = minimal response; NTX = N-terminal cross-linking protein of type-1 collagen; PD = progressive disease; PE = physical examination; PEP = protein electrophoresis; PR = partial response; PT = prothrombin time; RFU = response follow-up; sCR = stringent complete response; SFU = safety follow-up; SPEP = serum protein electrophoresis; UPEP = urine protein electrophoresis; VGPR = very good partial response.

- a. Study visits will occur every other cycle beginning Cycle 12 (ie Cycle 12, 14, 16, etc).
- b. The Safety Follow-up visit will occur 30 days (±7 days) from the last dose of study drug or prior to the start of a new anticancer therapy. If subject withdraws consent to treatment, subject may still participate in safety follow-up.
- c. Subjects who permanently discontinue from the study for reasons other than PD will be followed every 2 months until PD or use of alternative antineoplastic therapy. During this period, myeloma assessment will be done per investigator discretion as referenced in [Section 7.1.4](#).

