8.8.3. Exploratory Efficacy Endpoints

8.8.3.1. Progression-free Survival (PFS)

PFS is defined as the duration from the start of study treatment to PD (earliest occurrence) or death (regardless of cause of death), whichever comes first. The calculation for the time of PD will be the same as that for DCB (Section 8.7.2.1).

PFS will be right-censored for subjects who meet one or more of the censoring conditions listed in Table 5 below.

Table 5: Date of Event and Censoring Rules for PFS Analysis

Row	Situation	Date of Event or Censoring	Outcome
Events include death or first documentation of confirmed PD that occurred on or prior to the data analysis cutoff date. For Cohorts 1 and 3 ibrutinib monotherapy, events need to meet one additional criterion: occurred at or prior to initiation of dexamethasone.			
1.1	Death or confirmed PD documented at scheduled disease assessments or between two scheduled disease assessments.	Earliest date of adequate disease assessment documenting confirmed PD or date of death due to progression, whichever occurs first.	Progressed
1.2	Death before first disease assessment	Date of death	Progressed
All other cases will be censored as follows:			
2.1	No baseline assessment	Date of first study treatment	Censored
2.2	No adequate post-baseline assessment (including lost to follow-up since enrollment)	Date of first study treatment	Censored
2.3	Not known to have confirmed PD or died at the data analysis cutoff date (this includes subjects who were known to have confirmed PD or died after the data analysis cutoff date)	Date of last adequate disease assessment showing no evidence of confirmed PD on or before data analysis cutoff date	Censored
2.4	Addition of dexamethasone (Cohorts 1 and 3 ibrutinib monotherapy only)	The start date of dexamethasone	Censored

For subjects who meet more than one censoring condition, PFS will be censored according to the earliest censoring condition. For subjects who meet none of the censoring conditions, PFS will be calculated using the earliest event date.

$\text{PFS Event (day)} = \text{Date of PFS event} - \text{Date of first study treatment}$

$\text{PFS Censor (day)} = \text{Date of censoring} - \text{Date of first study treatment} + 1$

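### Disease tests in Response Follow-up are optional although subjects are to be followed until PD, so censoring for PFS, TTP, DCB and DOR may be informative, in a direction that cannot be fixed in advance

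*Protocol*

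**What the plan says.** The synopsis (Study Design, Stage 2) states: "Subjects who discontinue study drug without PD will be followed for response until PD or start use of alternative antineoplastic therapy". Protocol 7.1.4 gives the same endpoint for follow-up and adds an interval: these subjects "will be followed for Response Follow-up (RFU) approximately every 2 months until PD or start use of alternative antineoplastic therapy".

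The next sentence of 7.1.4 begins "During this period, the following tests may be performed" and leaves the choice to the investigator, as standard of care. The list that follows covers SPEP, UPEP, immunofixation, FLC, immunoglobulins, plasmacytoma evaluation, bone radiology and chemistry including calcium. Appendix 4 footnote c repeats it: "During this period, myeloma assessment will be done per investigator discretion". The one firm commitment in 7.1.4 is "A bone marrow aspirate sample at the time of confirmed progression will be collected during this period", which applies only once progression has already been confirmed.

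The Appendix 4 grid pulls the other way. It carries a note that assessments go on until PD, and its M-protein row appears to have marks reaching the follow-up columns. The table's column alignment is not reliable in the copy reviewed, so the reading of the marks is uncertain.

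On the analysis side, a subject not known to have confirmed PD is censored under row 2.3 of SAP Table 4 (DCB) and Table 5 (PFS) at the "Date of last adequate disease assessment showing no evidence of confirmed PD on or before data analysis cutoff date". DOR and TTP take the DCB rules (SAP 8.8.2.3 and 8.8.3.2). SAP 6.2.1 imputes no missing efficacy values unless otherwise specified. No sensitivity analysis addresses missed assessments or stopping without PD.

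**The concern.** A subject can be followed to PD only if something capable of showing PD is measured. The PD criteria in Appendix 5 need an M-protein, FLC, marrow or calcium value, or evidence of a new plasmacytoma or bone lesion. In Response Follow-up none of these is required before progression is known. SAP 8.8.2.1 also requires confirmation of M-protein progression, so a single optional test may not yield an event.

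A subject who stops for toxicity or by choice and is not tested again is censored close to the time the drug is withdrawn; a similar subject at a site that keeps testing becomes an event. Kaplan-Meier treats the censored subject as progressing at the rate of those still under observation, most of whom are on drug. If that is wrong, the estimates are biased, and by an amount that varies with site habit. With no control arm, the error cannot cancel in a comparison.

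At stake are two secondary endpoints (DCB, DOR), two exploratory endpoints (PFS, TTP), and the PFS landmarks that SAP 8.8.3.1 suggests at 4, 8, 12 and 16 months.

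**Working it through.** The plan gives no event count, power or expected value for these endpoints, so there is no figure of its own to reproduce. The check asks which way the bias runs and how large it could be.

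**Inputs, all assumptions unless noted.**
- On-drug median time to PD of 4 months. Protocol 2.5 cites TTP of 2.8 to 4.7 months, but for high-dose dexamethasone.
- 25% stop drug without PD (also 15% and 35%). The documents give no share.
- Off-drug PD hazard k times the on-drug hazard.
- No optional test is done, and censoring is at stopping.
- n=43, the maximum for an expanded cohort in the protocol; also n=18, the planned first stage of Cohorts 2 to 4.

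**Formulas.** With exponential times, h = ln 2/4 = 0.1733 per month. If 25% stop first, the stopping hazard is d = h × 0.25/0.75 = 0.0578.
- True PFS: S(t) = e^(−(h+d)t) + [d/(h+d−kh)] × [e^(−kht) − e^(−(h+d)t)].
- Kaplan-Meier with censoring at stopping estimates e^(−ht).
- Large-sample Greenwood variance: e^(−2ht) × [h/(h+d)] × [e^((h+d)t) − 1]/n.

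**At 8 months.** e^(−ht) = 0.25 and e^(−(h+d)t) = 0.1575.
- k=1.5: 0.1575 − 2 × (0.125 − 0.1575) = 0.222
- k=2: 0.1575 − 0.5 × (0.0625 − 0.1575) = 0.205
- k=3: 0.1575 − 0.2 × (0.0156 − 0.1575) = 0.186
- k=1: 0.250, so no bias
- k=0.67: 0.277, so Kaplan-Meier is 2.7 points too low

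Greenwood SE at n=43: √(0.0625 × 0.75 × 5.35/43) = 0.076. At n=18 it is 0.118.

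| k | KM minus true | SEs, n=43 | SEs, n=18 | True median (KM 4.0) |
|---|---|---|---|---|
| 1.5 | +2.8 points | 0.4 | 0.2 | 3.8 |
| 2 | +4.5 points | 0.6 | 0.4 | 3.7 |
| 3 | +6.4 points | 0.8 | 0.5 | 3.5 |

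For k from 1.5 to 3, 15% stopping gives +1.6 to +3.7 points (0.2 to 0.5 SE at n=43), and 35% gives +4.1 to +9.4 points (0.5 to 1.1 SE).

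**With visit timing.** A simulation of 200,000 subjects per scenario used 28-day assessments on drug, a disease test at the 30-day safety visit, and complete 2-monthly testing as the reference. Assumptions here: median 5 months, 30% stopping without PD. The table shows 12-month progression-free estimates.

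| k | All tests done | No follow-up tests, row 2.3 | PD found late (mean delay 4 months) |
|---|---|---|---|
| 0.67 | 0.238 | 0.190 (−0.05) | 0.271 (+0.03) |
| 1 | 0.202 | 0.183 (−0.02) | 0.242 (+0.04) |
| 1.5 | 0.169 | 0.176 (+0.01) | 0.212 (+0.04) |
| 2 | 0.148 | 0.169 (+0.02) | 0.190 (+0.04) |

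When tests are simply absent, the sign changes with k. When PD is found late, the estimate is too long at every k tried. The median was 5.52 months in most of the 5-month scenarios, with or without the tests.

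**The case against.** The case against has four main parts.

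First, a reader might infer that all four endpoints must come out too long. The documents do not support that. Row 2.3 censors at the last adequate assessment, so a missed progression does not by itself add progression-free time. Upward bias needs faster progression off drug or late detection; the documents establish neither, and the calculations show a bias of zero or the opposite sign otherwise. This part stands.

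Second, a reader might infer that everyone who dies becomes an event. That is true only for PFS. For DCB, DOR and TTP, death from causes other than progression is censored (SAP Table 4 row 2.5). This stands. Tables 4 and 5 do, however, have no row for missed assessments, so a death due to progression after an untested gap is an event at the death date, later than the true progression.

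Third, the synopsis and 7.1.4 are not rival follow-up rules. Both say until PD or new therapy, and the synopsis prescribes no tests. This too stands. The mismatch is between that stated aim, together with the Appendix 4 grid, and the discretionary wording in 7.1.4 and footnote c. Repeat bone imaging is not mandated on treatment either, so its being optional later is no new gap.

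Fourth, the size is a worst case: 7.1.4 describes the tests as standard of care, so some will be done, and the safety visit appears to include a disease test. DCB and DOR rest on responders only, and 8 CBRs is the success threshold in Cohorts 2 to 4, so imprecision would outweigh this bias. These limits are fair. They reduce the likely size but do not remove the dependence on site practice.

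**Conclusion.** The point holds as one of incomplete ascertainment and possibly informative censoring. Followed as written, the plan leaves detection of progression after stopping drug without PD to each site, and the SAP neither repairs nor tests this.

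The likely direction is upward if subjects progress faster once off drug or if progression is found late. It is not certain: there is little or no bias at equal hazard, and estimates can be too short if progression is slower.

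The size is modest. With an on-drug median of 4 months, 25% stopping without PD, an off-drug hazard 1.5 to 3 times on-drug and no tests done, 8-month PFS is about 3 to 6 points too high. That is 0.4 to 0.8 Greenwood SE at n=43 and 0.2 to 0.5 at n=18. Median PFS moves by 0.2 to 0.5 months in that model. None of these inputs is a trial figure, and DCB and DOR were not modelled separately.

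The primary CBR analysis and the sample size are not affected. This is an inexpensive improvement to secondary and exploratory endpoints, not a flaw in the main test.

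**What to change.** **Protocol.** Reconcile the synopsis, 7.1.4, the Appendix 4 grid and footnote c. At each existing 2-monthly Response Follow-up visit, require the one test by which the subject's disease was measurable at baseline (SPEP, UPEP or serum FLC). Leave the other tests optional.

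**SAP 8.8.2.1 and 8.8.3.1.** Add a sensitivity analysis that counts discontinuation without PD and without a later disease assessment as an event, and report it beside the main PFS, TTP, DCB and DOR estimates. If the safety visit carries a disease test, define later as after that visit, and place the event where row 2.3 would otherwise censor. Label the result a conservative bound.

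**Cost.** One routine blood or urine test per visit already scheduled, for those subjects who stop without PD, plus a repeat where M-protein progression needs confirming; a wording change; and one extra analysis run. The bound is biased short, because it treats every untested subject as progressing at once, and should not replace the main estimate. If the protocol can no longer change, the SAP analysis alone costs only programming.
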